13.5 Expected AE and RAE Collection and Reporting

The requirements for reporting RAEs will begin when the participant provides informed consent and will end 30 days after the participant's involvement in the study has ended. Expected AEs will be assessed every four weeks post-randomization. Figures 5a-d provide algorithms describing the reporting process.

Figure 5a. Collection and Reporting Process for Expected AEs

[figure not shown]

Figure 5b. Collection and Reporting Process for RAEs Collected during Standardized Telephone Interviews

Blinded evaluator administers the Reportable Adverse Events Form at a scheduled 4-week telephone interview

Event is identified by the participant or proxy & meets the criteria for an RAE

Blinded evaluator completes a Reportable Adverse Event Record for each event and submits documentation to the clinical site coordinator

Has the RAE been previously reported?

Clinical site coordinator records RAE ID#, marks as duplicate, and files in participant binder

Clinical site coordinator assigns new RAE ID#, and records event on the RAE Log in the participant binder

Clinical site coordinator notifies clinical site PI and clinical site clinician immediately

Clinical site PI (or designee) redacts documents to conceal treatment assignment and notifies the CCC in writing (by fax or email) within 24 hours of the event being reported to the PI

CCC NOTIFIES DSMB AND NIA IN WRITING (BY FAX OR EMAIL) WITHIN 24 HOURS OF THE EVENT BEING REPORTED TO THE CCC

LEGEND

Clinical Site Staff

Site Coordinator

CCC

Figure 5c. Collection and Reporting Process for RAEs Identified Anytime Other than During a Standardized Telephone Interview

[figure not shown]
[figure not shown]

Figure 5d. CCC Reporting Process for RAEs

Timeline for Reporting Events

The RAE reporting schedule is shown below:

1. RAEs will be reported to the clinical site PI and clinical site clinician as soon as the event is known.
2. The clinical site PI (or designee) will redact documents to conceal treatment assignment and report all RAEs to the CCC in writing (by fax or email) within 24 hours of the event being reported to the investigator.
3. The CCC will report all RAEs to the DSMB and NIA in writing (by fax or email) within 24 hours of being notified.
4. The DSMB and NIA will receive notification about all RAEs within 48 hours of when the event is known and reported by study staff.

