The other reason that we are proposing the use of TENS is to assist in pain management. Herrick et al (2004) grouped persons with hip fracture as moderate/severe or mild/no pain.⁹⁷ Forty-two percent of the sample reported moderate/severe pain at baseline. The other benefit of TENS will be to reduce pain which may lead to an increased activity level. TENS has been demonstrated to be effective in managing both acute and chronic pain for a number of conditions. Cheing and Hui-Chan (2004), for example, reported that TENS alone applied to persons with chronic pain secondary to knee osteoarthritis resulted in an increase in knee ROM during walking and increased gait speed.⁹⁸ TENS was compared with a sham control after surgical repair of hip fracture. When TENS was applied after surgery, pain on movement was reduced and health-related quality of life improved.⁹⁹ Gorodetskyi (2007) compared the effect of electrical stimulation to a sham control in 60 older people during acute hospitalization following hip fracture repair.¹⁰⁰ Participants receiving electrical stimulation reported substantially and significantly less interference from pain on walking ability after each of the 10 sessions. Pain

scores, which decreased over the 10-day treatment period in both groups, were also markedly less in the electrical stimulation group. The two studies that have examined the use of TENS for pain alleviation have not, however, examined its effect on alleviation of the chronic pain reported by persons after hip fracture.

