6.1 Overview of Study Design

A RCT of 210 older adults who have experienced a hip fracture will be carried out at three clinical sites (AU, UMB, and UCHC) with half of the subjects receiving a specific multi-component intervention (PUSH) and the other half receiving a non-specific multicomponent intervention (PULSE). Randomization of 210 participants meeting eligibility criteria will take place after post-acute rehabilitation ends, up to 26 weeks after admission to the hospital for hip fracture. The primary endpoint will be measured 16 weeks after randomization. Patients age 60 and older who have had surgical repair for hip fracture will be identified at the three clinical sites through a variety of recruitment sources and will be evaluated for eligibility. Following consent to participate, eligible participants will undergo a comprehensive baseline assessment and will then be randomized to one of the two treatment groups. The cohort will be measured again 16 weeks post-randomization. Figure 1 shows the sequence of participant contacts from the time of hospitalization until the final assessment approximately 16 weeks after randomization.

Figure 1. Timeline for screening, randomization, and follow-up

Within a week of randomization, participants will initiate the intervention with a PT in their place of residence and receive counseling with a registered dietician. The follow-up assessment will take place 16 weeks post-randomization. Telephone interviews will be conducted every four weeks, beginning four weeks post-randomization, to obtain information about RAEs and expected AEs, and to help reduce loss to follow-up by maintaining ongoing rapport with participants. An honorarium will be given at the completion of both study assessment visits.

For participants randomized prior to version 10.0 of the protocol, follow-up assessment visits occurred 16 weeks and 40 weeks from the date of randomization and telephone interviews were conducted every four weeks during the 40-week study period for a total of 10 telephone interviews.

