10.6.4 Expected Adverse Events (AEs)

Expected AEs will be assessed every four weeks during the telephone interview. Participants (or their proxies) will be asked a series of standardized questions related to pain (feet, hip, back, knees); breathing problems or chest pain; skin irritations, rash, or skin tears; numbness or tingling; and falls (with and without injury).

Section 11: Study Procedures

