11.1 Baseline Assessments

The baseline assessments will be performed immediately following screening for phase 3 criteria. The following measures will be assessed at the baseline visit.

- Baseline Weight, Height, and Body Mass Index*
- Demographics and Blood Draw Information*
- Modified Mini-Mental State Examination*
- Six-Minute Walk Test*
- Baseline Interview
- Activities-Specific Balance Confidence†
- Short Physical Performance Battery
- SF-36 Health Survey†
- Modified Physical Performance Test
- Yale Physical Activity Survey†
- Weight and Quadriceps Strength†
- Center for Epidemiologic Studies-Depression scale
- Pepper Assessment Tool for Disability†
- Mini Nutritional Assessment-Short Form
- Life Orientation Test-Revised
- Brief Resilience Scale

* Collected as part of phase 3 screening

† Eliminated from baseline assessment in protocol version 11.0

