11.3 Telephone Interviews

Structured telephone interviews with blinded assessors will be conducted every four weeks for 16 weeks post-randomization starting four weeks after the date of randomization. Participants will be given a health diary at the baseline visit to assist with recall during the telephone interviews. The following measures will be administered:

- Reportable Adverse Events (RAE) Form
- Health Care Utilization questionnaire[†]
- Expected Adverse Events (AE) Form
- Self-report of study medication adherence[†]

[†] Eliminated from telephone interview in protocol version 11.0

Note: The subset of participants enrolled prior to protocol version 10.0 received telephone calls every four weeks for 40 weeks post-randomization using all the measures listed above.

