13.2 Classifying Adverse Events

An AE is any unfavorable or unintended medical occurrence in a human study participant that has taken place during the course of a research project, including any abnormal sign, symptom, or disease, whether or not related to participation in the research

For the purposes of this study, any event that meets the criteria for an SAE, is unexpected, or results in injury to the participant while s/he is under the supervision of study related personnel will be classified as an RAE.

Adequate review, assessment, and monitoring of RAEs require that they be classified as to severity, expectedness, and potential relatedness to the study intervention.

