13.8 Reporting Expected AEs and RAEs to the DSMB

The DSMB will review tabulated data on non-serious and expected AEs on a semi-annual basis and monitor for adverse event rates out of proportion to those expected. The CCC will forward the individual Reportable Adverse Event Records, including a narrative for each event, as well as a table showing all RAEs to the DSMB and NIA semi-annually. The DSMB will review all RAEs that are temporally related to the interventions in aggregate form at its scheduled meetings.

All RAEs that relate to hazards of the study interventions or are cause for urgent concern will be reported to the CCC and the CCC will report these to the DSMB chairman, NIA, and the UMB IRB immediately after recognition of their importance. If the DSMB chairman concludes that an RAE is of universal and immediate concern, the CCC will notify local clinical sites at once. The DSMB chairman may recommend convening the DSMB to review participant safety based on any individual report or accumulating evidence, including evidence according to treatment assignments.

Section 14: Intervention Discontinuation

Certain RAEs may result in a temporary interruption or early discontinuation of the trial assessments and interventions or components of these assessments and interventions. Please refer to the appropriate MOP chapter(s) for specific instructions on stopping criteria during screening, intervention, and follow-up assessments.

After such RAEs occur, a participant may resume the trial intervention when the clinical site clinician and the primary care provider (if participant has one) agree that it is appropriate. For mild problems that require temporary cessation of intervention, the clinical site investigator, in consultation with the clinical site clinician and participant, may agree to reintroduce the participant to the study intervention.

At any time, the DSMB may recommend discontinuation of any component or intervention group of the study for any of the following reasons:

- 1) Compelling evidence from this or any other study of an adverse effect of the study intervention(s) that is sufficient to override any potential benefit of the interventions to the target population.
- 2) Compelling evidence from this or any other study of a significant beneficial effect of the study intervention(s), such that its continued denial to other study group(s) would be unethical.

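### The expected-AE items have no baseline value and no new-or-worse condition, so persisting post-fracture pain cannot be separated from new or worsened pain, and arm differences may be diluted or confounded with pain relief from TENS.

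*Protocol*

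**What the plan says.** **Timing.** Protocol 13.5: "Expected AEs will be assessed every four weeks post-randomization". Protocol 11.3: "Structured telephone interviews with blinded assessors will be conducted every four weeks for 16 weeks post-randomization starting four weeks after the date of randomization". Table 1 allows the first call from one week before to three weeks after its target, which is week 3 to week 7. Protocol 6.1 places treatment earlier: "Within a week of randomization, participants will initiate the intervention with a PT".

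**Content.** Sections 10.6.4 and 13.3 list foot, hip, back and knee pain, breathing problems, chest pain, skin problems, numbness or tingling, and falls.

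**Baseline.** Section 11.1 opens with "The following measures will be assessed at the baseline visit". The list that follows has neither the Expected AE Form nor a site-specific pain item. It does include a Baseline Interview, whose content is not given.

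**Definition.** Section 13.2 describes an AE as an unfavourable or unintended occurrence "that has taken place during the course of a research project, including any abnormal sign, symptom, or disease". It sets no condition of onset or worsening after randomisation. Section 13.2.2 counts as expected an event attributable to the participant's underlying condition.

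**Use.** Under 13.8 the DSMB sees tabulated data twice a year and is to "monitor for adverse event rates out of proportion to those expected". No reference rate is given. The SAP contains no adverse-event analysis.

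**Background rate.** Section 5.3 says of a cited hip-fracture cohort: "Forty-two percent of the sample reported moderate/severe pain at baseline".

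**The concern.** Many participants will enter with hip, knee or back pain left over from the fracture and surgery. If they report it at week 4, nothing in the plan shows whether it began after treatment started, became worse, or never changed. The same holds for numbness.

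This trial is exposed to that ambiguity in two ways. PUSH is resistance and aerobic training, for which new musculoskeletal pain is an obvious non-serious harm. PULSE includes TENS, which section 9.4 says is meant to reduce pain. The arms may therefore differ both in new pain and in relief of old pain, and a symptom report after randomisation adds the two together. The DSMB could miss an excess of new pain in one arm, or could read pain relief in PULSE as harm from PUSH. A baseline that was not collected cannot be recovered at analysis.

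**Working it through.** The documents give no expected-AE rate and plan no test of one, so there is no stated figure to reproduce. What follows is an illustration of size.

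**Inputs from the Protocol**
- 105 per arm (15.6.1) and 6.8% loss to follow-up (15.6.1), so n = 105 × 0.932 = 97.9 per arm.
- b = 0.42, the pain prevalence in the cohort cited in 5.3. It is not a figure from this trial or for one pain site, so 0.20 and 0.60 are also shown.

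**Assumed, with no source in the documents**
- New onset among those symptom-free at baseline: 10% in PULSE, 25% in PUSH.
- A share s of baseline pain persists. First s = 1 in both arms.

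**Formulas**
- Proportion reporting the symptom: q = b·s + (1 − b)·(new onset).
- Z = difference / √[(p₁(1−p₁) + p₂(1−p₂)) / n]. Power at two-sided 0.05 = Φ(Z − 1.96).

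**No baseline, b = 0.42**
- PULSE: 0.42 + 0.58 × 0.10 = 0.478. PUSH: 0.42 + 0.58 × 0.25 = 0.565.
- Difference 8.7 points; ratio 0.565 / 0.478 = 1.18, against a true new-onset ratio of 2.5.
- Z = 0.087 / 0.0711 = 1.22; power 23%.
- Share of reporters whose pain is pre-existing: 0.42 / 0.478 = 88% in PULSE and 0.42 / 0.565 = 74% in PUSH.

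**Symptom-free at baseline only, b = 0.42**
- n = 97.9 × 0.58 = 56.8 per arm, 10% vs 25%.
- Z = 0.15 / 0.0699 = 2.15; power 57%.

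**New onset counted over all participants, b = 0.42**
- 0.58 × 0.10 = 5.8% vs 0.58 × 0.25 = 14.5%. The difference is again 8.7 points.
- Z = 0.087 / 0.0427 = 2.04; power 53%. The gain over 23% comes from removing the persistent reports, which add variance and no contrast.

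**Range over prevalence**

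| b | No baseline | Power | Symptom-free n per arm | Power |
|---|---|---|---|---|
| 0.20 | 28.0% vs 40.0% | 43% | 78 | 71% |
| 0.42 | 47.8% vs 56.5% | 23% | 57 | 57% |
| 0.60 | 64.0% vs 70.0% | 14% | 39 | 43% |

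Full persistence does not drive this. With s = 0.7 in both arms and b = 0.42, the reports are 35.2% vs 43.9%, still 8.7 points apart.

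**Opposite direction.** Assume new onset of 10% in both arms, with baseline pain persisting in 60% of PULSE and 90% of PUSH.
- PULSE: 0.42 × 0.6 + 0.58 × 0.10 = 31.0%. PUSH: 0.42 × 0.9 + 0.58 × 0.10 = 43.6%.
- An apparent PUSH excess of 12.6 points, with no difference in new pain. At b = 0.20 the excess is 6.0 points, and at b = 0.60 it is 18.0 points.

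**What can still be gained at this version.** The summary of changes for version 11.0 expected about 160 randomised by the time of approval, which leaves at most about 210 − 160 = 50, or 25 per arm.
- Symptom-free at b = 0.42: 25 × 0.932 × 0.58 = 13.5 per arm.
- Z = 0.15 / 0.143 = 1.05; power about 18% (a rough figure at this sample size).

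**The case against.** **The form is not shown.** Its wording, the content of the Baseline Interview and Figure 5a are all absent. The form may ask only about new or worse symptoms, and an occurrence that takes place during the project can be read as excluding unchanged pain. This stands: a reader might infer that unchanged hip pain is counted as an AE at every call, and the documents do not show that. They show only that nothing in the protocol prevents it.

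**Other records exist.** Health questions open each PT session (9.5.3), PTs submit a form for each visit and keep logs (10.6.1), RAEs are asked about before PT visits (10.6.3), Table 3 has an alert for new acute musculoskeletal pain, and 13.2.2 makes an expected event reportable when its severity or frequency exceeds what was anticipated. This also stands. The expected-AE interview is not the only systematic record of non-serious harm, although it is the one that blinded assessors administer in standard form to both arms.

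**Some baseline pain data exist.** SF-36 bodily pain was collected at baseline from participants consented before version 11.0, and exclusion 6.10 removes those with severe pain during the baseline walk. These help in part. The first is not site-specific and has been dropped; the second leaves milder pain in.

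**Randomisation balances baseline pain in expectation.** This is correct. With equal persistence the result is lost sensitivity, not a biased direction.

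**The numbers are assumed.** Also correct. The onset and persistence rates have no source, no such test is planned, and the calculation models new onset only, whereas the remedy covers new or worse symptoms.

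**Conclusion.** The gap is real and modest. The expected-AE items are first asked after treatment has started, they are not listed at baseline, and the definition lacks a new-or-worse condition. As the plan is written, persisting pain cannot be separated from new or worsened pain. The point is strongest for the pain items, applies to numbness, and hardly touches falls and other discrete events.

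A reader might infer that the design hides real differences between arms. The documents do not support that as a certainty: the effect may be dilution, or it may be a spurious contrast if TENS relieves existing pain. At 42% persisting prevalence and 10% vs 25% new onset, power is 23% without a baseline and 57% among those symptom-free at baseline. Both figures rest on assumed rates and on every participant having a baseline value. They show the mechanism and are not the gain achievable now, since about three-quarters of the sample (160/210 = 76%) was expected to be randomised before version 11.0 took effect.

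**What to change.** - Add the Expected AE items to 11.1, asked once at the baseline visit before randomisation.
- In 13.3 and 13.8, define a treatment-emergent expected AE as a listed symptom that is new or worse than at baseline.
- Tabulate for the DSMB, by arm, the number of participants with at least one such event, and give all reports in a second table.
- If the form or the Baseline Interview already records onset or baseline symptoms, say so in 13.3; that would largely close the point.

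The cost is a few minutes at an existing visit and one more form. The limitation is that participants already randomised (about 160 of 210 expected by version 11.0) have no baseline value on these items and must be shown separately. For those consented before version 11.0, baseline SF-36 bodily pain is a partial substitute: it can stratify the pain tables by any prior pain, but not by site.

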13.6 Evaluation and Follow-up of RAEs

All RAEs submitted to the CCC will be forwarded to a blinded ISM for adjudication and follow-up. The ISM may contact the clinical site coordinator to request additional information from the participant, significant other, or their health care provider and may seek medical records from a physician or care setting if needed to make a determination about relatedness to the study. If the event is potentially related to the study, the ISM will contact the clinical site PI who will consider whether the event was listed in the protocol and ICF and whether modifications to the protocol and ICF should be considered. To ensure the appropriate classification of events, the clinical site clinician and/or clinical site PI may also be called on to provide additional information.

The ISM will be responsible for providing follow-up for ongoing reportable events, as follows:

1. The ISM will follow up on RAEs until a final status has been determined for the event (e.g., recovered, ended in death, is still present, or status is unknown). Some RAEs may have a status of still present at the conclusion of the study. These are the categories of RAE status:
 - a. 'Resolved' is an event that has ended, with or without residual deficits.
 - b. 'Still present' is an event that is ongoing.
 - c. 'Unknown' should be used when the site is unable to make contact with the participant or proxy or to obtain additional information in any other way.
 - d. 'Died' is for an event that ended in death.
2. If there are follow-ups to an event (and the event is ongoing), the ISM will use the Reportable Event Evaluation and Follow-up Form to record the event follow-up and submit to the CCC.
3. Once the event is no longer ongoing and a final status for the event has been determined, the ISM will record the final status, enter the closed date, and sign and date the Reportable Adverse Event Evaluation and Follow-up Form that will be submitted to the CCC.

The CCC will be responsible for reporting RAEs to the DSMB, NIA, and clinical sites, as needed. Clinical sites will be responsible for reporting RAEs to their respective IRBs according to local requirements.

13.6.1 Action Taken

The clinical site PI, in consultation with the study clinician and the ISM, will decide whether or not an RAE requires that the participant be removed from the study intervention and will forward the decision to the CCC. The DSMB will be notified of the recommended course of action by the CCC. Actions taken in response to the RAE will fall into one of five categories:

- Study intervention modified
- Study intervention suspended temporarily
- Study intervention stopped permanently
- Study assessment modified
- No action taken

13.7 Responsibilities

Clinical site PIs have primary responsibility for the safety of participants as it relates to the study protocol. Clinical site coordinators will be responsible for reviewing RAEs and assuring accurate and timely reporting of RAEs. Clinical site clinicians will be responsible for reviewing RAEs before they are sent to the CCC. Blinded ISMs will evaluate and classify RAEs and provide follow-up for events until they are resolved. The DSMB will be responsible for reviewing monitoring data for evidence of harm attributable to participation in CAP.

13.7.1 Clinical Site Clinician

The clinical site clinician will be available by telephone for consultation with study personnel during all time periods when participants are engaged in the home-based interventions or at clinical assessment sites. In addition, the clinical site clinician will be responsible for reviewing and RAEs requiring immediate notification of the IRB and CCC and for being “on call” for study-related emergencies. The clinical site clinician may delegate responsibilities related to immediate notification to a “covering” clinician.

